APPENDIX 1: STUDY FLOW CHART

APPENDIX 2: SUMMARY PROTOCOL

Trial Title	Revascularisation for Ischaemic Ventricular Dysfunction (REVIVED-BCIS2)
Aim	To evaluate the efficacy and safety of percutaneous coronary intervention (PCI) compared to optimal medical therapy (OMT) alone for ischaemic left ventricular dysfunction
Trial Design	Multicentre prospective randomised open controlled trial
Primary Endpoint	All-cause death or hospitalisation due to heart failure
Secondary Endpoints	Quality of life score:
	Kansas City Cardiomyopathy Questionnaire (KCCQ)
	EuroQol EQ-5D-5L
	New York Heart Association (NYHA) Functional Class
	Left ventricular ejection fraction (LVEF) on echocardiography at 6 months and 1 year
	Hospitalisation for heart failure
	All-cause death
	Cardiovascular death
	Acute myocardial infarction (MI)
	Appropriate implantable cardioverter defibrillator (ICD) therapy
	Unplanned further revascularisation
	Canadian Cardiovascular Society (CCS) angina class
	Health resource use
	Brain natriuretic peptide (BNP or NT-proBNP) level
	Troponin (T or I) level
	Major bleeding
Inclusion Criteria	LVEF ≤35%
	Extensive coronary artery disease (CAD)
	Viability in at least 4 dysfunctional myocardial segments, that can be revascularised by PCI
Major Exclusion	Acute MI <4 weeks prior to randomisation (clinical definition)
Criteria	Acutely decompensated heart failure requiring treatment with inotropes/ventilation/mechanical circulatory support <72 hours prior to randomisation
	Any contraindication to PCI

Sample Size and	n=700
Enrolment	Start date: 1 st June 2013
	Recruitment start date: 1 st September 2013
	Recruitment end date: 19 th March 2020
	Follow-up end date: 31 st March 2022
	Number of centres: 40 (listed on trial website)

APPENDIX 3: TRIALS PROCEDURES

	Tests required for eligibility	Baseline	Pre-PCI as per local protocol #	At discharge (up to 16 hours) post-PCI #	48 hrs post-PCI ‡	At 6 months after randomisation	At 1 year after randomisation	At 2 years after randomisation	Yearly follow-up	End of trial follow-up
Clinical assessments	(standard	of care)	1				ı	Г		ı
Demographics and medical history	х									
Coro Angio	х									
Viability assessment	х									
LVEF Assessment	Х*									
Echo		Χ [†]								
ICD check		Х				Х	х	Х		
FBC	Х			х						
Creatinine	х			х						
HbA1C		Х								
Full Lipid Profile		Х								
СК			х	х						
Trop T/I		Х	х	х		х	х			
ECG		Х		х						
AKI					х					
Trial specific assessn	nents		ı	ı			ı	I		1
Echo						х	х			
BNP / NT-proBNP		х				х	х	x		
NYHA/CCS		Х				х	х	Х		
EQ-5D-5L		Х				х	х	х	Х	х
KCCQ		Х				х	х	х		
Primary Endpoint				х		х	х	х	Х	х
Secondary Endpoints						х	х	х	х	
SAEs				х		х	х	х		
Cardiac Medication is staged, please col		x	6.1	x		х	х	х		

[‡] If PCI is staged, please collect for each stage of the procedure

^{*} In the case of patients with Acute Coronary Syndrome (ACS), must be >4 weeks after ACS

[†] This echo is only required if there is no available echo within 6 months of randomisation and >4 weeks after ACS

REVIVED Viability Study Statistical Analysis Plan

Study Title: Revascularisation for Ischaemic Ventricular Dysfunction (REVIVED-BCIS2)

Study Registration Number: ISRCTN45979711 / NCT01920048

Statistical Analysis Plan Authors: [name], [name], [name], [name], [name]

[name], [name], [name]

Statistical Analysis Plan Version: 2.0 dated 12th December 2022

CURRENT VERSION APPROVED BY (IF CHANGED):

Name	Signature	Date
[name]	DocuSigned by:	12/12/2022
[name]	Docusigned by:	12/12/2022

VERSION CI	HRONOLOGY:		
VERSION NUMBER	EFFECTIVE DATE	REASON(S) FOR CHANGE	AUTHORISED BY (NAME)
1.0	29/05/2022	NA	[name] [name]

Version 1 of the SAP was signed off prior to database lock and unblinding of the main trial results.

Version 2 of the SAP was signed off prior to database lock and unblinding of the imaging core laboratory results.

2. Background

REVIVED-BCIS2 is a multicentre randomised controlled trial investigating whether percutaneous coronary intervention (PCI) improves clinical outcomes in patients with severe left ventricular dysfunction, extensive coronary artery disease and demonstrable myocardial viability, compared with optimal medical therapy (OMT) alone¹. The primary outcome of the trial is a combination of all-cause and hospitalisation for heart failure (HHF) at a minimum of 2 years follow-up. Key secondary outcomes include change in left ventricular ejection fraction (LVEF) from baseline to 6- and 12-month follow up, as well as the occurrence of myocardial infarction, quality of life scores and healthcare resource utilisation. Enrolment in the trial required demonstration of significant myocardial viability, defined as at least four dysfunctional-but-viable segments which could be revascularised by PCI. Viability needed to be assessed by one of the following 4 modalities: cardiac magnetic resonance imaging (CMR), dobutamine stress echocardiography (DSE), single positron emission computed tomography (SPECT) or positron emission tomography (PET); given wide availability in the United Kingdom, most viability studies were performed with CMR and DSE. When assessing eligibility for enrolment in REVIVED, adjudication of segmental viability was done by recruiting centres, with the trial protocol providing guidance for the definition of viability by each modality.

Viability is defined as regions of dysfunctional myocardium in which function is predicted to improve following appropriate treatment; this has typically been considered specific to revascularisation. Viability assessment with CMR is largely performed with late gadolinium enhancement (LGE) sequences, where myocardial scar is identified by persistent enhancement following injection of gadolinium contrast. Scar burden has been shown to inversely relate to the likelihood of improvement in function at both a segmental and global level². With stress echocardiography, viability is determined by the presence of contractile reserve in response to dobutamine stress, in

myocardial segments which are dysfunctional at rest³. The presence of extensive viability is thought to identify patients who gain particular benefit from undergoing revascularisation, though previous studies have been inconclusive and no high-quality data exists to support this presumption^{4–6}.

3. Study objectives

3.1.1. Primary

To determine whether the extent of viability predicts the effect of PCI on clinical outcomes and left ventricular functional recovery in patients with severe ischaemic cardiomyopathy.

3.1.2. Secondary

To determine the accuracy with which viability imaging predicts global functional recovery

To explore the relationship between viability, revascularisation, functional recovery, and clinical outcome.

4. Data available

4.1. Sample size

In REVIVED-BCIS2 all patients underwent viability imaging prior to randomisation; at least four viable segments which could be revascularised by PCI were required for inclusion. Of the 700 patients enrolled, viability was assessed with CMR in 491 and DSE in 187. Primary outcome data are available for 99.1% of patients. Serial echocardiographic data are available for a subset of these patients.

4.2. Imaging processing

All viability studies will be analysed by one of two dedicated core laboratories: the King's College London Imaging Sciences CMR core laboratory (led by [name]) and the King's Health Partners Stress Echo core laboratory (led by [name]). Analyses will be performed by trained readers blinded to trial-group assignment and any other clinical data. Viability will be analysed on a segmental basis, using the AHA 17-segment model, excluding segment 17 (the left ventricular apex) as it is incompletely imaged on DSE and not included in CMR quantification. Transthoracic echocardiograms were analysed by the Guy's and St Thomas' echocardiography core laboratory with readers also blinded to the temporal sequence of echocardiograms.

4.3. Other datasets

The following additional datasets will provide comparative data for analysis:

- REVIVED-BCIS2 main trial database and electronic case report forms (London School of Hygiene and Tropical Medicine)
 - o All analyses will be based on the intention-to-treat population
- REVIVED-BCIS2 echocardiography core lab database (Guy's and St Thomas' NHS Foundation Trust)
- REVIVED-BCIS2 arrhythmia case report form (King's College London)

5. Definitions

5.1. Wall motion scoring

For CMR and DSE, wall motion score will be classified on a five-point ordinal Likert scale as 1 – normal, 2 – hypokinetic, 3 – akinetic, 4 – dyskinetic, 5 – aneurysmal. For GSTT echocardiography core laboratory (non-DSE) measurements, the latter two points are combined into one category.

5.2. CMR - segmental scar transmurality

Segmental scar transmurality is assessed visually on an ordinal scale as 0%, 1-25%, 26-50%, 51-75% and 76-100% of the segmental extent LGE. For trial inclusion, viability was adjudicated according to local protocols, with a recommendation that dysfunctional segments with \leq 25% transmurality be considered viable, \geq 50% non-viable and 25-50% based on local expert opinion. For core-laboratory adjudication, segmental viability was defined as a scar transmurality \leq 25% in a segment which is dysfunctional at rest[2,7,8]. Sensitivity analyses will also be performed using a cut-off of \leq 50%.

5.3. DSE – contractile reserve

Viability is defined as the presence of contractile reserve in a segment which is dysfunctional at rest. Contractile reserve is defined as an improvement in wall motion score ≥ 1 grade (or ≥ 2 grades in segments which are dyskinetic at rest) during dobutamine stress, compared to baseline.

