10.6. Angiography core lab

Both pre-randomisation and trial procedure coronary angiogram and angioplasty images will be transferred to an angiography core laboratory (at Golden Jubilee National Hospital, Glasgow, UK) via anonymised optical media. Each participant's pre-randomisation BCIS-1 JS and PCI procedural success will be independently validated by the core laboratory. The core laboratory will calculate a number of other scores reflecting the anatomic complexity of coronary disease, the extent of effective revascularisation and the complexity of CTO lesions.

This data will be used to conduct a number of sub-analyses to identify predictors of benefit for the primary and secondary outcomes. The core laboratory will subsequently provide the relevant data to the Sponsor and CTU at the London School of Hygiene & Tropical Medicine for analysis against the data held in the eCRF.

11. Assessment of Viability

Eligibility for the trial will require demonstration of myocardial viability in at least 4 dysfunctional myocardial segments, subtended by diseased coronary arteries that can be treated by PCI.

Regional function at rest will be scored according to the American Heart Association 17 segment-5 grade scoring model (1: normal; 2: mildly hypokinetic; 3: severely hypokinetic; 4: akinetic; 5: dyskinetic)(43). Segments with resting wall motion abnormalities (grade 2-5) will be considered dysfunctional.

Segmental viability can be determined by any imaging modality. The criteria for determining viability will be based on local protocols and as determined by the local imaging specialist,

using all available information; the following are guidelines for defining segmental viability in the REVIVED trial:

- DSE: improvement in contraction by at least one wall motion grade during low-dose Dobutamine stimulation, compared to resting wall motion (improvement by at least 2 grades if aneurysmal or dyskinetic at rest).
- MRI: ≤25% transmural late gadolinium-enhanced (LGE) images. Adjudication of viability in segments with 26-50% transmurality will be at the discretion of the recruiting centres, on the basis of other available information, including of contractile reserve during low-dose Dobutamine stimulation.
- SPECT: tracer activity on the delayed images that is ≥50% of the activity in the segment with maximal activity (in rest-redistribution protocols).
- PET: perfusion metabolism (FDG) mismatch.

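### The core-lab DSE rule asks for a two-grade improvement in dyskinetic but not in aneurysmal segments, so the worse resting grade faces the easier viability test

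*Protocol*

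**What the plan says.** The Viability Study SAP gives one wall motion scale for CMR and DSE in section 5.1: "1 – normal, 2 – hypokinetic, 3 – akinetic, 4 – dyskinetic, 5 – aneurysmal". The two worst grades are pooled only for other readings: "For GSTT echocardiography core laboratory (non-DSE) measurements, the latter two points are combined into one category". For DSE they therefore remain distinct.

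Section 5.3 then sets the core-lab rule: "Viability is defined as the presence of contractile reserve in a segment which is dysfunctional at rest". The threshold for calling reserve present follows next: "Contractile reserve is defined as an improvement in wall motion score ≥ 1 grade". A bracketed exception is attached to it: "or ≥ 2 grades in segments which are dyskinetic at rest". Aneurysmal segments are not mentioned.

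Protocol section 11 (Assessment of Viability) also gives a DSE criterion, under the introduction "the following are guidelines for defining segmental viability in the REVIVED trial". Its general threshold is again one grade, but the exception covers both states: "improvement by at least 2 grades if aneurysmal or dyskinetic at rest".

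The resulting count of viable segments enters as a linear term in the Cox model for the primary outcome and in its interaction with treatment (Viability SAP 7.1). It is also used in the analyses of ejection fraction recovery (7.2), and these are repeated on DSE data alone in Appendix 2 (9.1).

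**The concern.** On the SAP's own scale, aneurysmal is worse than dyskinetic. One would expect the criterion for viability to be at least as demanding there. As written it is less demanding: the aneurysmal segment needs one grade and the dyskinetic segment needs two. A segment can then be called viable although at stress it has only reached the state that, had it been the resting state, would have triggered the stricter test.

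The count of viable segments is the exposure in the viability study. A rule that credits segments with the poorest resting motion too easily can only add to that count. Someone applying 5.3 literally and someone applying the protocol's wording would also get different counts from the same scan.

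**Working it through.** The point concerns a classification rule, so the plan has no figure to reproduce. The check is to list every possible improvement and apply both wordings.

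**Inputs**
- Scale: grades 1 to 5 (Viability SAP 5.1). Dysfunctional at rest means grade 2 or worse.
- Rule A (Viability SAP 5.3): viable if rest minus stress is at least 1, or at least 2 when the resting grade is 4.
- Rule B (wording of protocol section 11, applied to the SAP scale): viable if rest minus stress is at least 1, or at least 2 when the resting grade is 4 or 5.

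**All ten improvements from a dysfunctional resting grade**

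| Rest to stress | Grades gained | Rule A | Rule B |
|---|---|---|---|
| 2 to 1 | 1 | viable | viable |
| 3 to 2 | 1 | viable | viable |
| 3 to 1 | 2 | viable | viable |
| 4 to 3 | 1 | not viable | not viable |
| 4 to 2 | 2 | viable | viable |
| 4 to 1 | 3 | viable | viable |
| 5 to 4 | 1 | **viable** | **not viable** |
| 5 to 3 | 2 | viable | viable |
| 5 to 2 | 3 | viable | viable |
| 5 to 1 | 4 | viable | viable |

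Nine of the ten agree. The one that differs is aneurysmal to dyskinetic. The incoherence also shows within the Rule A column alone: 5 to 4 passes and 4 to 3 fails, each with a gain of one grade.

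**How many segments could be exposed**
- DSE patients: 187 of 700 (Viability SAP 4.1). This is an upper bound, because CMR is used where both scans are interpretable (5.4) and unusable studies are excluded (6.4).
- Segments read per patient: 16, since segment 17 is left out (4.2). 187 × 16 = 2,992 DSE segments.
- The documents do not say how many are aneurysmal. If 1% to 3% were (an assumption, not a figure from the documents), that would be 0.01 × 2,992 ≈ 30 to 0.03 × 2,992 ≈ 90.
- That range counts all aneurysmal segments. Only those improving by exactly one grade are misclassified, so 30 to 90 is a ceiling under the assumption, not an estimate.
- Against all CMR and DSE segments, (491 + 187) × 16 = 10,848, the ceiling is 30/10,848 ≈ 0.3% to 90/10,848 ≈ 0.8%.

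**The case against.** **Dyskinetic may have been meant to include aneurysmal.** This is possible, but the documents do not say so, and 5.1 points the other way: it separates the two for DSE and pools them only for non-DSE echo readings. If the inclusive meaning was intended, 5.3 should state it.

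**The protocol wording does not bind the core laboratory.** This stands. Section 11 offers guidelines for local adjudication of eligibility, and 5.3 is a separate core-lab definition. The scales also differ: the protocol's runs from normal through mild and severe hypokinesia to akinetic (4) and dyskinetic (5), with no aneurysmal grade, so applying its wording to the SAP scale is itself an interpretation. A reader might infer a breach of the protocol, but the documents support only an unexplained difference between two definitions. For CMR, by contrast, SAP 5.2 sets the local recommendation beside the core-lab cut-off and adds a sensitivity analysis. The incoherence within the SAP does not depend on the protocol at all.

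**The effect is confined.** This also stands. CMR-only analyses do not use 5.3, and Cox models of viability adjust for modality (6.3). The scans precede randomisation (4.1) and readers are blinded to assignment (4.2), so any misclassification should not differ by arm.

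**Conclusion.** The rule in 5.3 is wrong as written: it misclassifies one transition, aneurysmal to dyskinetic, and sets an easier test for the worse resting state. The error runs one way, adding viable segments. It reaches only DSE-classified patients, at most 187 of 700. Its size in the data cannot be worked out, because neither the number of aneurysmal segments nor the share improving by exactly one grade is given. On the assumed prevalence it is probably small in the pooled analyses. It would be most visible where DSE is analysed alone, since no CMR counts dilute it there.

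Three stronger readings are tempting and are not supported:
- A reader might infer bias in the interaction between viability and PCI. Neither a direction nor a size for such bias follows from the documents, and the misclassification is not expected to depend on arm.
- A reader might infer that patients could be carried over the entry requirement of four viable segments. Eligibility was adjudicated locally before randomisation, and the core-lab count enters the main model linearly with no cut at four.
- A reader might infer that dyskinetic and aneurysmal should be pooled for DSE. Pooling with a two-grade test would also turn 5 to 3 into non-viable, although that change gains two grades and meets the protocol's wording on the SAP scale. It would contradict 5.1 as well.

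**What to change.** Reconcile protocol section 11 with Viability SAP 5.1 and 5.3. The minimum change is to extend the two-grade exception in 5.3 to segments that are either dyskinetic or aneurysmal at rest, leaving the five-point DSE scale as it is. Then re-derive the DSE viable-segment counts from the resting and stress grades. If the difference from the protocol is intended, 5.3 should say so and give the reason.

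It would also help to report how many segments change class, so that readers can see the size of the effect.

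The cost is a few words and a re-run of the derivation. No scan needs to be read again, provided both grades were recorded for each segment.

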5.4. Patients with CMR and DSE data

Where participants underwent both CMR and DSE data prior to randomisation, both scans are available and both are interpretable, the CMR data will be used in all analyses.

5.5. Echocardiography – left ventricular morphology and function

Core lab adjudicated resting transthoracic echocardiography-derived values will be used to determine left ventricular volumes and ejection fraction for all analyses that combine or compare CMR and DSE datasets. CMR-derived volumes will be used for analyses restricted to baseline CMR datasets.

6. Outcomes

6.1. Primary outcome

The primary composite outcome is as specified in the main trial SAP and protocol: all-cause death or hospitalisation for heart failure. Analysis will be by the time-to-first event on an intention-to-treat basis.

6.2. Secondary outcomes

While several secondary clinical outcomes were specified in the main trial protocol, for the Viability Study SAP, these will be restricted to all-cause death, cardiovascular death and heart failure hospitalisation, each analysed in the same manner as the primary composite outcome. Improvement of left ventricular function at six months is the key secondary outcome and will be defined in a binary manner, as an improvement in LV ejection fraction greater than the median change in LVEF at six months.

6.3. Comparison of CMR and DSE as viability tests

An exploratory analysis will be used to compare patients who underwent viability testing with DSE and CMR, as well as sensitivity analyses restricted to each modality, for the key outcomes above. Demographic details will be displayed for the two groups as either frequency and percentage, mean \pm standard deviation or median (and inter-quartile range) depending on the type of data and normality of distribution. All Cox models concerning myocardial viability will be adjusted for the testing modality used.

6.4. Missing data

Missing viability data will not be imputed – participants whose viability studies are either not available or are not suitable for analysis will be excluded. For patients who have survived more than 6 months, missing values of ejection fraction will be imputed using multiple imputation by chained equations

with randomised treatment, age, sex, and baseline, 6-month and 12-month ejection fraction included in the imputation model. Twenty imputed datasets will be generated and effect estimates and corresponding confidence intervals calculated using Rubin's rules. Other rules for handling missing data will follow the main trial SAP. A sensitivity analysis will be performed limited to patients who have echocardiography data available at baseline and 6-months.

7. Statistical analysis

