10.2. Baseline echocardiogram

If the qualifying echocardiogram study (TTE or resting images from a stress echo) was performed less than 6 months before randomisation, this study can also be submitted to the core lab to calculate baseline LVEF.

If the qualifying echocardiogram was done more than 6 months before randomisation, or the qualifying LVEF was assessed using MRI, a further transthoracic echocardiogram should be carried out soon after randomisation and this study submitted to the core lab to calculate baseline LVEF.

10.3. Qualifying EF flowchart:

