7.1. Viability and event-free survival

A Cox proportional hazards model will be used to assess the relationship between the number of viable myocardial segments (treated as a linear effect) and the primary outcome. Multivariable Cox analyses will be used to adjust the analysis for factors including age, sex, previous hospitalisation for heart failure, presence of diabetes, ejection fraction, extent of coronary disease, presence of chronic renal failure and modality of viability testing. The interaction between viability and treatment assignment on event-free survival will then be assessed using a Cox proportional hazards model containing the following covariates: viability (treated as a linear effect), randomly assigned treatment, and their interaction, plus the aforementioned list of baseline risk factors. In secondary analyses, the extent of viability will be divided into tertiles and Kaplan-Meier curves stratified by both viability tertile and treatment assignment presented. A sensitivity analysis will be performed where viability is defined irrespective of resting dysfunction (including segments with normal function at rest and with \$25% scar on CMR or contractile reserve on DSE).

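### Viability SAP 6.4 restricts imputation of ejection fraction to patients alive beyond 6 months, leaving no rule for a missing baseline EF in early deaths within the EF-adjusted Cox models of 7.1

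*Protocol*

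**What the plan says.** Viability Study SAP, section 6.4, sets the imputation rule: "For patients who have survived more than 6 months, missing values of ejection fraction will be imputed using multiple imputation by chained equations". EF at all three visits, baseline among them, enters the chained equations, and the only other terms named are treatment arm, age and sex. The rule is not confined to follow-up EF or to the functional-recovery analyses. Other missing-data rules are referred to the main trial SAP. One sensitivity analysis is named, restricted to patients with echo data at both baseline and 6 months.

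Section 7.1 adjusts the primary-outcome Cox model for "age, sex, previous hospitalisation for heart failure, presence of diabetes, ejection fraction, extent of coronary disease", renal failure and testing modality. The viability-by-treatment model then contains viability, treatment and their interaction, "plus the aforementioned list of baseline risk factors".

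Section 5.5 fixes the source of EF for analyses that combine or compare CMR and DSE data: "Core lab adjudicated resting transthoracic echocardiography-derived values will be used to determine left ventricular volumes and ejection fraction".

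Protocol section 10.2 allows the baseline echo to come after randomisation. If the qualifying LVEF was by MRI, or the qualifying echo was more than 6 months old, "a further transthoracic echocardiogram should be carried out soon after randomisation and this study submitted to the core lab".

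**The concern.** A condition on surviving 6 months is reasonable when EF is a 6-month outcome, as in the recovery analyses. Here the same condition also governs a baseline covariate in models that start at randomisation. Take two patients with the same missing baseline echo. The one alive at 6 months has EF imputed and stays in. The one who died by then has no stated route into the model.

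The gap could be linked to early death itself, because a baseline echo arranged after randomisation may never be done in a patient who dies soon afterwards. Every patient lost this way has a primary event. The interaction model affected is the one that serves the study's primary objective (section 3.1.1), so its analysis set should not depend on the outcome, even if the numerical effect is modest.

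**Working it through.** **1. Does any stated rule fill the gap?**

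| Possible rule | What it covers | Fills baseline EF for a death by 6 months? |
|---|---|---|
| Viability SAP 6.4, multiple imputation | Patients alive beyond 6 months | No |
| Viability SAP 6.4, referral to the main SAP; main SAP 6.5.2 | Imputation is something to be considered, according to the scale and pattern of missingness | No fixed rule |
| Main SAP 9.2.1, 0% for deaths | LVEF as the 6-month and 1-year outcome | No; 0% has no meaning at baseline |
| Viability SAP 7.3, event-free at 6 months | Stated for 7.3 only | Not applicable; 6.1 makes the primary outcome time to first event by intention to treat |
| Viability SAP 6.4, sensitivity analysis | Needs a 6-month echo as well | No; it also excludes every death by 6 months |

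A Cox fit omits records with a missing covariate unless the analyst intervenes, so the default result is exclusion.

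**2. Is the imputation model adequate where it does apply?** As listed, it holds treatment, age, sex and the three EF values. It omits the event indicator, the cumulative hazard and the number of viable segments, although the imputed baseline EF then enters a Cox model with those terms.

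**3. How many patients?** The documents give no figure for deaths by 6 months or for missing baseline EF, so this is a range under assumptions.

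- Cohort (Viability SAP 4.1): 491 CMR + 187 DSE = 678, before unreadable scans are removed.
- Annual hazard, assumed constant: h = -ln(1 - p)/t, using mortality quoted in the protocol background (2.3 and 2.4).
- Deaths by 6 months: 678 × (1 - exp(-0.5h)).
- Share of these without baseline EF: assumed 10%, 30% or 50%.

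| Source | p, t | h | Deaths by 6 months | Lost at 10% | 30% | 50% |
|---|---|---|---|---|---|---|
| Earlier PCI cohort | 33%, 51 months | 0.094 | 31 | 3 | 9 | 16 |
| Surgical trial, OMT arm | 41%, 4.7 years | 0.112 | 37 | 4 | 11 | 19 |
| Surgical trial, medically treated patients, as quoted in 2.4 | 46%, 56 months | 0.132 | 43 | 4 | 13 | 22 |

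As a cross-check, the 6-month mortality of 6% quoted for the earlier PCI cohort gives 678 × 0.06 = 41 deaths, inside this range.

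The planned 300 events give a scale. That figure reproduces: power = Φ(√(300/4) × |ln 0.7| - 1.96) = Φ(3.09 - 1.96) = 87%, against a stated figure of over 85%. In proportion, 300 × 678/700 = 291 events. A loss of 3 to 22 is then about 1% (3/291) to 7.5% (22/291) of events.

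**4. What would it do to the estimates?** The adjusted interaction model was simulated with 678 patients, proportional hazards, a 2-year event rate of 36% and about 39 deaths by 6 months.

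- Missingness equal in both arms, removing from 4 to all 39 of the early deaths: the treatment log hazard ratio moved by at most about 0.005, and the viability and interaction coefficients by less than 0.001.
- Missingness of 30% (PCI) against 10% (OMT) among early deaths, and 50% against 10%: the treatment log hazard ratio moved by about -0.02 and -0.04, that is a factor of exp(-0.02) = 0.98 to exp(-0.04) = 0.96 in PCI's favour. The interaction coefficient moved by at most 0.003.

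The simulated follow-up yields more events than 291, and neither an early PCI hazard nor missingness that depends on viability was simulated. The shifts are therefore indicative only.

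**The case against.** The strongest reply is that the SAP nowhere says these patients are excluded. It refers other missing-data questions to the main SAP, which leaves room for imputation, and the survival clause reads naturally as being about EF as the 6-month outcome. It is true that exclusion is an inference from how a Cox model treats missing covariates. But the main SAP fixes nothing for a baseline covariate, and the survival clause is worded to cover EF in general. What remains is a gap that would have to be settled by an unrecorded choice after the data are seen.

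Other analyses do keep these patients: the first Cox model in 7.1, without EF, and the Kaplan-Meier curves. CMR-only analyses may also have another source, since 5.5 uses CMR-derived volumes there and 8.1.1 lists CMR ejection fraction. This limits the point to the EF-adjusted models on combined data and to others that rely on the echo value.

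Three stronger readings are tempting and are not supported.

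- **That the 491 CMR patients all had a post-randomisation echo.** The 491 counts the viability test. Protocol 10.2 turns on how LVEF was qualified and how old the echo was; a patient with CMR viability and a recent qualifying echo needs no further scan. The number with MRI-qualified LVEF is not given.
- **That the loss biases the viability-by-treatment interaction towards PCI.** Losing more deaths in the PCI arm moves the treatment effect. The interaction moves only if the loss also varies with viability, and nothing in the documents suggests that.
- **That the rule by itself breaks an otherwise complete intention-to-treat set.** Section 6.4 already openly excludes patients without analysable viability studies. The narrower complaint stands: that exclusion does not depend on survival, and this one does.

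**Conclusion.** The point holds as a gap in the rule. As written, section 6.4 leaves a missing baseline EF without a stated remedy in patients who died by 6 months. Standard fitting would then remove them from the EF-adjusted Cox models in 7.1 while keeping survivors with the same gap.

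The likely size is about 3 to 22 patients, all with a primary event. This rests on a constant hazard taken from mortality quoted in the protocol and on an assumed 10% to 50% of early deaths lacking baseline EF. If few or no early deaths lack it, the effect disappears.

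The bias is probably small: negligible for the interaction in the settings examined, and a treatment-effect shift of about 2% to 4% on the hazard-ratio scale only if losses are clearly greater in the PCI arm. The case for changing the text is that selection on the outcome is avoidable at no cost and that the one sensitivity analysis named in 6.4 would not reveal it. The conclusions are not shown to be at risk.

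**What to change.** Amend Viability SAP 6.4 as follows.

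- Impute missing baseline EF for every patient with analysable viability data, whatever their survival.
- Include in the imputation model the event indicator, cumulative hazard, number of viable segments, randomised treatment and its interaction with viability, and the other Cox covariates from 7.1.
- Use site-reported qualifying LVEF or CMR-derived EF as auxiliary variables.
- Keep the 6-month survival condition for follow-up EF only.
- Report the number with missing baseline EF by arm and by survival at 6 months, so that the reader can judge the size directly.

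The cost is SAP wording and a slightly larger imputation model. No new data and no extra patients are needed.
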